## 5.9. Safety Analyses

All the safety analyses will be performed based on Safety Population.

### 5.9.1. Study Drug Exposure

Study drug exposure will be summarized based on Safety Population. The summary will include duration of treatment, number of infusions, the number of cycles received per patient, cumulative dose, cumulative dose level, weekly dose intensity, relative dose intensity, by dose cohort and combination arm. Details of study drug administration will be included in patient listings.

Dose modifications and delays will also be summarized.

The exposure formulas are defined below.

#### Olaratumab:

- Duration of treatment (weeks) = ([Date of last dose – date of first dose] + 21) ÷ 7
- Cumulative dose (mg) = Sum of all doses
- Cumulative dose level (mg/kg) = Sum of (dose administered at each infusion [mg] ÷ Last available weight [kg] prior to that infusion)
- Weekly dose intensity (mg/kg/week) = (Cumulative dose level) ÷ (Duration of Treatment )
- Planned weekly dose intensity (mg/kg/week) (depending on the cohort)
  - Part A = 10 mg/kg/week
  - Part B = (2 x 20 mg/kg) / 3 weeks = 40/3 mg/kg/week
- Relative dose intensity (%) = (Weekly dose intensity) ÷ (Planned weekly dose intensity) x 100

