
Part B patients will be treated for 1 cycle (21 days) of olaratumab monotherapy at 20 mg/kg on Day 1 and Day 8 then receive olaratumab (20 mg/kg) plus one of 3 standard chemotherapy regimens described in Part A. Part B will be complete when at least 10 patients (regardless of assigned chemotherapy arm) are evaluable for safety of olaratumab 20 mg/kg monotherapy. Part C will be initiated when at least 10 patients (regardless of chemotherapy arm) are evaluable for safety of olaratumab 20 mg/kg from Part B. Part C patients will receive olaratumab (20 mg/kg) in combination with any of the 3 chemotherapy regimens (per investigator discretion) from Cycle 1 onward (i.e no olaratumab monotherapy in Cycle 1 of Part C). Parts B and C together will enroll up to 45 patients (15 per chemotherapy arm). Treatment will continue until disease progression or other discontinuation criteria are met.

Diagnosis and Main Criteria for Inclusion and Exclusions: Eligible patients will be <18 years of age with a diagnosis of relapsed or refractory solid tumors not amenable to curative treatment, for whom chemotherapy with doxorubicin, vincristine/irinotecan, or high-dose ifosfamide is deemed appropriate by the investigator. In addition, the patient must have adequate performance status by Lansky or Karnofsky and adequate hematologic, organ, and coagulation function. The patient must not have a hematologic malignancy, uncontrolled intercurrent illness, or active infection.

Test Product, Dosage, and Mode of Administration:

Olaratumab: for intravenous (IV) use, supplied in single-use 500 mg/50 mL vials containing 10 mg/mL of product in histidine buffer, administered to patients as an IV infusion at 15 or 20 mg/kg on Day 1 and Day 8 of each cycle. Cycles are 21 days in length.

Doxorubicin: will be administered intravenously. Doxorubicin (37.5 mg/m²) is to be administered on Day 1 and Day 2 of each 21-day cycle, for up to 6 cycles or a cumulative dose of 450 mg/m².

Dexrazoxane: may be administered at a 10:1 ratio (dexrazoxane:doxorubicin) at the investigator's discretion via IV injection, beginning 30 minutes prior to each doxorubicin infusion for the prevention of cardiotoxicity. It is recommended that all patients receiving doxorubicin also receive dexrazoxane. Dexrazoxane should be administered after completion of the olaratumab infusion, prior to administration of doxorubicin.

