Cycle 1	Olaratumab ^a	Part A	15 mg/kg	IV approximately 1 hour infusion on Day 1 and Day 8 of each 21-day cycle
		Part B	20 mg/kg	
Cycle 2-n	Olaratumab ^a	Part A	15 mg/kg	IV approximately 1 hour infusion on Day 1 and Day 8 of each 21-day cycle
		Part B	20 mg/kg	
1-hour observation period^b followed by				
	Doxorubicin ^{c,dg}	Parts A and B	37.5 mg/m ²	IV Day 1 and Day 2 of each 21-day cycle
OR				
	Vincristine ^e	Parts A and B	1.5 mg/m ²	IV Day 1 and Day 8 of each 21-day cycle
	Irinotecan ^g	Parts A and B	50 mg/m ²	IV Days 1, 2, 3, 4, and 5 of each 21-day cycle
OR				
	Ifosfamide ^{fg}	Parts A and B	2.8 g/m ²	IV approximately 2 to 3 hour infusion on Days 1, 2, 3, 4, and 5 of each 21-day cycle

Abbreviations: eCRF = electronic case report form; IV = intravenous.

- a Administer premedication prior to infusion of olaratumab. Recommended premedication agents include histamine H1 antagonists such as diphenhydramine hydrochloride (or equivalent). Additional premedication may be provided at the investigator's discretion. Premedication must be provided in the setting of a prior Grade 1-2 infusion-related reaction, as detailed in Section 7.2.4.1. All premedication administered must be adequately documented in the eCRF.
- b A 1-hour observation period is required after the administration of the first and second doses of olaratumab. If there is no evidence of an infusion-related reaction during the initial 2 cycles of olaratumab, then no observation period is required for subsequent treatment cycles. In the event an infusion-related reaction occurs thereafter, then the 1-hour observation period should be reinstated; see Section 7.2.4.1.
- c Administer doxorubicin for up to 6 cycles only or cumulative dose of 450 mg/m².
- d Administer doxorubicin according to institutional guidelines and/or clinical practice as an IV injection or as an infusion in less than 60 minutes (+10 minutes). Decrease the rate of doxorubicin administration if erythematous streaking along the vein proximal to the site of infusion or facial flushing occurs.
- e For patients weighing less than 10 kg, the dose of vincristine should be 0.05 mg/kg. The dose is capped at 2 mg for all patients.
- f Administer ifosfamide for up to 6 cycles only or a cumulative dose of 84 g/m². Treatment beyond 84 g/m² requires consultation with the Lilly clinical research physician/clinical research scientist.

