#### Doxorubicin:

- Duration of treatment (weeks) = ([Date of last dose – date of first dose] + 21) ÷ 7
- Cumulative dose (mg) = Sum of all doses
- Cumulative dose level (mg/m^2) = Sum of (dose administered at each infusion [mg] ÷ Last available body surface area [BSA] [m^2] prior to that infusion)
- BSA (m^2) = 0.007184 \* weight (kg) ^0.425 \* height (cm) ^0.725

- Weekly dose intensity (mg/m^2/week) = (Cumulative dose level) ÷ (Duration of treatment)
- Planned weekly dose intensity (mg/m^2/week) = 2 x 37.5 mg/m^2/ 3 weeks=25
- Relative dose intensity (%)=(Weekly dose intensity) ÷ (Planned weekly dose intensity) x 100

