#### Vincristine:

- Duration of treatment (weeks) = ([Date of last dose – date of first dose] + 21) ÷ 7
- Cumulative dose (mg) = Sum of all doses
- Cumulative dose level (mg/m^2) = Sum of (dose administered at each infusion [mg] ÷ Last available body surface area [BSA] [m^2] prior to that infusion)
- BSA (m^2) = 0.007184 \* weight (kg) 0.425 \* height (cm) 0.725
- Weekly dose intensity (mg/m^2/week) = (Cumulative dose level) ÷ (Duration of treatment)
- Planned weekly dose intensity (mg/m^2/week)
  - If patient baseline weight >10kg: = 2 x 1.5 mg/m^2/ 3 weeks=1
  - If patient baseline weight <10kg: =2 x 0.05/3 weeks=1/30
- Relative dose intensity (%)=(Weekly dose intensity) ÷ (Planned weekly dose intensity) x 100

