#### Ifosfamide:

- Duration of treatment (weeks) = ([Date of last dose – date of first dose] + 21) ÷ 7
- Cumulative dose (g) = Sum of all doses
- Cumulative dose level (g/m^2) = Sum of (dose administered at each infusion [g] ÷ Last available body surface area [BSA] [m^2] prior to that infusion)

- BSA (m^2) = 0.007184 \* weight (kg)  $^{0.425}$  \* height (cm)  $^{0.725}$
- Weekly dose intensity (g/m^2/week) = (Cumulative dose level)  $\div$  (Duration of treatment )
- Planned weekly dose intensity (g/m^2/week) = 5 x 2.8 g/m^2/ 3 weeks=14/3
- Relative dose intensity (%)=(Weekly dose intensity)  $\div$  (Planned weekly dose intensity) x 100

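### SAP 5.9.1 understates relative dose intensity for fully dosed patients (75% after one olaratumab cycle) and overstates it more than tenfold for vincristine under 10 kg

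*SAP*

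**What the plan says.** SAP 5.9.1 defines duration of treatment identically for olaratumab, doxorubicin, vincristine, irinotecan and ifosfamide: last dose date minus "date of first dose] + 21) ÷ 7". Weekly dose intensity is cumulative dose level over that duration, and RDI is weekly intensity over planned weekly intensity.

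The planned values each divide one cycle's dose by three weeks. Olaratumab in Part A is 10 mg/kg/week, and for Part B the SAP has "Part B = (2 x 20 mg/kg) / 3 weeks = 40/3 mg/kg/week". Doxorubicin is "2 x 37.5 mg/m 2 / 3 weeks=25" and ifosfamide "5 x 2.8 g/m 2 / 3 weeks=14/3".

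None of these drugs has its last dose of the cycle on Day 1. The protocol synopsis describes olaratumab as "administered to patients as an IV infusion at 15 or 20 mg/kg on Day 1 and Day 8 of each cycle". Protocol 7.2.2 puts vincristine on Days 1 and 8, irinotecan and ifosfamide on Days 1 to 5, and doxorubicin on Days 1 and 2.

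For vincristine, the SAP's cumulative dose level is "Sum of (dose administered at each infusion [mg] ÷ Last available body surface area [BSA"], so it is in mg/m² for every patient. The planned value for small children is "If patient baseline weight <10kg: =2 x 0.05/3 weeks=1/30". Its source is footnote e to Protocol Table JGDN.7.1: "For patients weighing less than 10 kg, the dose of vincristine should be 0.05 mg/kg".

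**The concern.** There are two separate faults.

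**Time base.** Adding 21 days to a last dose given on Day 8, 5 or 2 counts the final cycle as 28, 25 or 22 days. The planned intensity counts it as 21. A patient dosed fully and on schedule cannot reach 100%, and the shortfall depends on the drug and on the number of cycles received. Early stopping is foreseeable: Protocol 6.2.2 provides for Part A and B patients who complete Cycle 1 and go no further, and Protocol 8.3 schedules scans every two cycles. Because SAP 5.9.1 tabulates exposure by dose cohort and chemotherapy arm, a cohort whose patients stop sooner will look under-dosed even if no dose was missed.

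**Units.** For vincristine under 10 kg, the numerator is mg/m²/week and the denominator is mg/kg/week, under a heading that says mg/m²/week. The ratio has no meaning as a percentage. Such patients are within scope: Protocol 5.1 describes enrolment from age 0, the creatinine limits in Protocol 6.1.1 start at 1 month, and there is a dedicated dosing rule below 10 kg.

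**Working it through.** **1. The SAP's planned values reproduce.** Doses per cycle × dose ÷ 3 weeks:

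- olaratumab: 2×15/3 = 10 and 2×20/3 = 40/3
- doxorubicin: 2×37.5/3 = 25
- vincristine: 2×1.5/3 = 1 and, under 10 kg, 2×0.05/3 = 1/30
- irinotecan: 5×50/3 = 250/3
- ifosfamide: 5×2.8/3 = 14/3

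The denominators are internally correct, and each assumes a 3-week cycle.

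**2. RDI of a fully dosed patient on the nominal schedule.** Let d be the last dosing day of the cycle and n the number of cycles. Duration as written is 21(n − 1) + (d − 1) + 21 = 21n + d − 1 days, so RDI = 21n/(21n + d − 1).

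| Drug | d | 1 cycle | 2 cycles | 6 cycles | 9 cycles |
|---|---|---|---|---|---|
| Olaratumab; vincristine at 1.5 mg/m² where the 2 mg cap does not bind | 8 | 21/28 = 75.0% | 42/49 = 85.7% | 126/133 = 94.7% | 189/196 = 96.4% |
| Irinotecan; ifosfamide (planned for up to 6 cycles) | 5 | 21/25 = 84.0% | 42/46 = 91.3% | 126/130 = 96.9% | 189/193 = 97.9% |
| Doxorubicin (up to 6 cycles) | 2 | 21/22 = 95.5% | 42/43 = 97.7% | 126/127 = 99.2% | – |

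Direct check for one olaratumab cycle: duration = 28/7 = 4 weeks. Part A: 30/4 = 7.5, and 7.5/10 = 75.0%. Part B: 40/4 = 10, and 10/(40/3) = 75.0%.

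**3. Two Part A patients who become indistinguishable.** The first receives both doses of one cycle: 30/4 = 7.5, so 75.0%. The second receives 3 of 4 doses over two cycles, with the last Day 8 dose omitted. The last dose is then on Cycle 2 Day 1, duration is (21 + 21)/7 = 6 weeks, and 45/6 = 7.5, so again 75.0%. The correct values are 100% and 75%.

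**4. Vincristine under 10 kg.** The documents give no heights or weights for such children, so body sizes are assumed. BSA uses the SAP formula, 0.007184 × weight^0.425 × height^0.725. One full cycle is two doses over 4 weeks as written.

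- 3.5 kg, 50 cm: BSA 0.209 m². Each dose is 0.05×3.5 = 0.175 mg = 0.839 mg/m². RDI = (2×0.839/4)/(1/30) = 1258%.
- 9.5 kg, 75 cm: BSA 0.428 m². Each dose is 0.475 mg = 1.110 mg/m². RDI = (2×1.110/4)/(1/30) = 1665%.

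After six cycles these become 1589% and 2103%. Wider assumed sizes (3 kg/48 cm to 9.9 kg/72 cm) give about 1190% to 1760% after one cycle.

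**5. Separating the two faults.** Correcting only the duration leaves 1678% to 2220% for the two children in step 4. Correcting only the units gives 75%. Correcting both gives 100%. With duration running to the end of the last 21-day cycle, every other drug also returns 100% after one cycle and after six.

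**The case against.** Last dose plus 21 days can be defended as a definition of treatment duration in its own right. Nothing in the documents makes 3.0 weeks the only proper answer for one cycle, and the general rule in SAP 5.3 would give 8/7 = 1.1 weeks from Day 1 to Day 8. That is fair, and it narrows the point: the fault is pairing this duration with a planned value built on 3 weeks per cycle, which makes weekly and relative dose intensity wrong.

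The 75% assumes exact Day 1 and Day 8 dosing. Protocol Attachment 1 allows ±3 days in Parts A and B, so with Day 1 fixed a fully dosed single cycle scores from 84.0% (Day 5: 21/25) to 67.7% (Day 11: 21/31). The figures are therefore nominal, but the understatement remains throughout the window.

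The shortfall shrinks with more cycles; for olaratumab it is 5.3 points after six. The vincristine percentages depend on assumed sizes, and there may be no patients under 10 kg in that arm. Both points stand, though every size tried gives a result more than ten times too high.

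SAP 5.7 separately reports omissions, reductions, delays and cycles, so a careful reader could see that dosing was complete. An RDI below 100% with no omissions is not by itself a contradiction, because delays also lower it. But that reader would have no explanation for 75% in a patient with no omission, reduction or delay. No other section of either document corrects the formulas.

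**Conclusion.** Both errors are present as written and should be corrected before the exposure table is produced.

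The time-base error affects all five drugs and every patient who receives the last planned dose of the final cycle. It is largest for the Day 8 drugs after a single cycle (a quarter of the true value) and small for doxorubicin (under 5 points after one cycle, under 1 after six). These sizes assume on-schedule, full dosing.

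The unit error is confined to vincristine patients under 10 kg, whose number the documents do not state. Where it applies, the reported percentage is unusable.

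The consequence is limited to descriptive exposure reporting. DLT rates, escalation decisions and the choice of recommended dose do not use these quantities.

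**What to change.** 1. **Duration.** For each drug, define duration in weeks as (Day 1 date of the patient's last cycle of that drug − date of first dose of that drug + 21)/7.
2. **Vincristine under 10 kg.** Compute cumulative dose level and weekly intensity in mg/kg, and compare them with 1/30 mg/kg/week. Set the basis infusion by infusion, because Protocol 7.2.2 recalculates doses after a 10% weight change and a child may cross 10 kg. One workable form expresses each dose as a fraction of the dose planned under the rule applied at that infusion, sums the fractions, and divides by 2 × weeks/3.
3. **While editing.** Tie planned olaratumab intensity to the assigned dose level. Only Part A and Part B values are listed, although SAP version 3 was issued to add Part C. With duration corrected, a fully dosed 10 mg/kg cohort would read (20/3)/10 = 66.7% against the Part A value, and patients enrolled at 15 mg/kg in Part B would read 10/(40/3) = 75.0%. Also confirm that the weight split covers a child of exactly 10 kg, as the protocol's rule does.

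The cost is a few formula edits in SAP 5.9.1 and reprogramming of one table. No new data are needed and no dose changes.

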#### Doxorubicin:

- Duration of treatment (weeks) = ([Date of last dose – date of first dose] + 21) ÷ 7
- Cumulative dose (mg) = Sum of all doses
- Cumulative dose level (mg/m^2) = Sum of (dose administered at each infusion [mg] ÷ Last available body surface area [BSA] [m^2] prior to that infusion)
- BSA (m^2) = 0.007184 \* weight (kg) ^0.425 \* height (cm) ^0.725

- Weekly dose intensity (mg/m^2/week) = (Cumulative dose level) ÷ (Duration of treatment)
- Planned weekly dose intensity (mg/m^2/week) = 2 x 37.5 mg/m^2/ 3 weeks=25
- Relative dose intensity (%)=(Weekly dose intensity) ÷ (Planned weekly dose intensity) x 100

#### Vincristine:

- Duration of treatment (weeks) = ([Date of last dose – date of first dose] + 21) ÷ 7
- Cumulative dose (mg) = Sum of all doses
- Cumulative dose level (mg/m^2) = Sum of (dose administered at each infusion [mg] ÷ Last available body surface area [BSA] [m^2] prior to that infusion)
- BSA (m^2) = 0.007184 \* weight (kg) 0.425 \* height (cm) 0.725
- Weekly dose intensity (mg/m^2/week) = (Cumulative dose level) ÷ (Duration of treatment)
- Planned weekly dose intensity (mg/m^2/week)
  - If patient baseline weight >10kg: = 2 x 1.5 mg/m^2/ 3 weeks=1
  - If patient baseline weight <10kg: =2 x 0.05/3 weeks=1/30
- Relative dose intensity (%)=(Weekly dose intensity) ÷ (Planned weekly dose intensity) x 100

#### Irinotecan:

- Duration of treatment (weeks) = ([Date of last dose – date of first dose] + 21) ÷ 7
- Cumulative dose (mg) = Sum of all doses
- Cumulative dose level (mg/m^2) = Sum of (dose administered at each infusion [mg] ÷ Last available body surface area [BSA] [m^2] prior to that infusion)
- BSA (m^2) = 0.007184 \* weight (kg) 0.425 \* height (cm) 0.725
- Weekly dose intensity (mg/m^2/week) = (Cumulative dose level) ÷ (Duration of treatment)
- Planned weekly dose intensity (mg/m^2/week) = 5 x 50 mg/m^2/ 3 weeks=250/3
- Relative dose intensity (%)=(Weekly dose intensity) ÷ (Planned weekly dose intensity) x 100

#### Ifosfamide:

- Duration of treatment (weeks) = ([Date of last dose – date of first dose] + 21) ÷ 7
- Cumulative dose (g) = Sum of all doses
- Cumulative dose level (g/m^2) = Sum of (dose administered at each infusion [g] ÷ Last available body surface area [BSA] [m^2] prior to that infusion)

- BSA (m^2) = 0.007184 \* weight (kg)  $^{0.425}$  \* height (cm)  $^{0.725}$
- Weekly dose intensity (g/m^2/week) = (Cumulative dose level)  $\div$  (Duration of treatment )
- Planned weekly dose intensity (g/m^2/week) = 5 x 2.8 g/m^2/ 3 weeks=14/3
- Relative dose intensity (%)=(Weekly dose intensity)  $\div$  (Planned weekly dose intensity) x 100

### 5.9.2. Adverse Events

Adverse events will be coded using the MedDRA dictionary. Severity grades will be assigned by investigators using the NCI-CTCAE Version 4.0.

The AE analysis variables have been specified in Section [5.3.1](#).

**Study drug-related AEs** are AEs that were considered to be at least possibly related to study drug by an investigator. Missing relationship is considered related to all study drugs.

The most current version of MedDRA at time of analysis will be used when reporting AEs by MedDRA terms. Unless otherwise specified, when summarized by PT, AEs will be presented in descending frequency of PT across treatment arms; when summarized by system organ class (SOC) and PT, AEs will be presented in descending frequency of PT within SOC across treatment arms. If more than one AE is recorded for a patient within any SOC or PT term, the patient will only be counted once on the most severe grade and the closest relationship to treatment.

Dose-limiting toxicities and DLT-equivalent toxicities will be listed by cohorts.

An overall summary of AEs will be provided to summarize the following categories using frequency counts and percentages by dose cohorts and combination arms:

- patients with at least one treatment-emergent adverse event (TEAE), serious adverse event (SAE), or CTCAE Grade 3 or 4 TEAE
- patients with AEs that led to death (all, up to 30 days after last dose of study drug), or discontinuation of study drug regimen

The summary will be provided for regardless of study drug causality, and repeated for events deemed by the investigator to be related to study treatment.

Treatment-emergent adverse events (TEAEs) will be summarized/listed as follows:

- treatment-emergent AE by system organ class (SOC) and PT
- study drug related TEAE
- summary of TEAEs by worst CTCAE grade
- consolidated TEAEs by consolidated category and PT
- study drug related consolidated TEAE

- summary of TEAEs by PT and descending frequency
- listing of TEAE leading to death (on treatment and within 30 days of last dose of study drug)
- listing of TEAE leading to discontinuation of olaratumab, chemotherapy, or any study drug
- listing of TEAEs leading to dose modification of any study drug, olaratumab, or chemotherapy

A patient listing of all AEs will be provided.

The following treatment-emergent SAE summaries will be provided:

- summary of treatment-emergent SAE by SOC and PT
- summary of study drug-related treatment-emergent SAE by SOC and PT
- summary of consolidated treatment-emergent SAEs
- summary of study drug-related consolidated treatment-emergent SAEs

A listing of SAEs will be produced.

The following death reports will be provided:

- summary of deaths (all deaths and deaths within 30 days of last dose of study drug)

The following AE of special interest (AESIs) summary will be provided:

- summary of treatment-emergent AESIs by AESI group and PT (regardless of causality and study drug-related)
- listing of treatment-emergent AESIs

### **5.9.3. Clinical Laboratory Evaluation**

The severity of laboratory results will be classified according to CTCAE Version 4.0. The shifts in CTCAE toxicity grading from baseline to worst postbaseline (first dose up to 30 days after the last dose of study treatment) grade will be produced.

A patient listing of all laboratory data will be provided with a flag for values outside of the laboratory normal range.

### **5.9.4. Vital Signs, Physical Findings, and Other Observations Related to Safety**

Actual value and change from baseline for vital sign measurements will be summarized at each assessment time point using summary statistics. Electrocardiogram, Echocardiogram(ECHO)/MUGA measurements will also be summarized at each assessment time point using summary statistics. Listings of vital signs, ECG, ECHO/MUGA and data will be provided.

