7.2.2. Dosing Schedule

If any study drug is discontinued (olaratumab or chemotherapy), the patient will be discontinued from the trial. A change of body weight $\geq 10\%$ (increase or decrease) from baseline will result in re-calculation of dose to be administered.

The following treatments will be administered in this study every 3-week (21-day) ± 3 day cycle ([Table JGDN.7.1](#) and [Table JGDN.7.2](#)).

Part A:

Cycle 1

Olaratumab as IV infusion on Day 1 and Day 8 (at 15 mg/kg)

Cycle 2 and beyond

Olaratumab as IV infusion on Day 1 and Day 8 (at 15mg/kg, or 10 mg/kg if de-escalated),

AND

Doxorubicin as IV infusion on Day 1 and Day 2 (at 37.5 mg/m²; up to 6 cycles or a cumulative dose of 450 mg/m²)

OR

Vincristine as IV on Day 1 and Day 8 (patients ≥ 10 kg: 1.5 mg/m², patients <10 kg: 0.05 mg/kg. Dose is capped at 2 mg) plus irinotecan as IV on Days 1, 2, 3, 4, 5 (at 50 mg/m²),

OR

Ifosfamide as IV on Days 1, 2, 3, 4, and 5 (at 2.8 g/m²; up to 6 cycles or a cumulative dose of 84 g/m²). Treatment beyond 84 g/m² requires consultation with the Lilly CRP/CRS.

Part B:

Cycle 1

Olaratumab as IV infusion on Day 1 and Day 8 (at 20 mg/kg)

Cycle 2 and beyond

Olaratumab as IV infusion on Day 1 and Day 8 (at 20 mg/kg),

AND

Doxorubicin as IV infusion on Day 1 and Day 2 (at 37.5 mg/m²; up to 6 cycles or a cumulative dose of 450 mg/m²)

OR

Vincristine as IV on Day 1 and Day 8 (patients ≥ 10 kg: 1.5 mg/m², patients <10 kg: 0.05 mg/kg. Dose is capped at 2 mg) plus irinotecan as IV on Days 1, 2, 3, 4, 5 (at 50 mg/m²),

OR

Ifosfamide as IV on Days 1, 2, 3, 4, and 5 (at 2.8 g/m²; up to 6 cycles or a cumulative dose of 84 g/m²). Treatment beyond 84 g/m² requires consultation with the Lilly CRP/CRS.

Part C:

All Cycles

Olaratumab as IV infusion on Day 1 and Day 8 (at 20 mg/kg),

AND

Doxorubicin as IV infusion on Day 1 and Day 2 (at 37.5 mg/m²; up to 6 cycles or a cumulative dose of 450 mg/m²)

OR

Vincristine as IV on Day 1 and Day 8 (patients \geq 10 kg: 1.5 mg/m², patients <10 kg: 0.05 mg/kg. Dose is capped at 2 mg) plus irinotecan as IV on Days 1, 2, 3, 4, and 5 (at 50 mg/m²),

OR

Ifosfamide as IV on Days 1, 2, 3, 4, and 5 (at 2.8 g/m²; up to 6 cycles or a cumulative dose of 84 g/m²). Treatment beyond 84 g/m² requires consultation with the Lilly CRP/CRS.

Table JGDN.7.1. Treatment Regimens/Dosing Schedule (Parts A and B)

Study Drug		Dose	Route	Timing

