7.2.4.2.2. Cardiac Monitoring for Doxorubicin-Associated Cardiotoxicity

Cardiotoxicity is a recognized risk of doxorubicin that increases with higher cumulative drug exposure. Cardiac monitoring is conducted by a combination of monitoring of clinical parameters, ECG, and ECHO / MUGA scan.

ECG changes, arrhythmias, tachycardia, and/or chest pain should be managed based on the specific findings.

An ECHO/MUGA scan is required within 28 days prior to first dose of study drug for all patients receiving doxorubicin. Thereafter, ECHO or MUGA scans must be performed at the end of Cycles 2, 4, and 6 and when clinically indicated. If doxorubicin cardiotoxicity has been observed, an ECHO or MUGA should be performed at the 30-day follow-up visit. Additional ECHO/MUGA may be performed if clinically indicated or at the investigator's discretion.

If there is a decrease in LVEF to or below 40% or an absolute decrease of 20%, then doxorubicin will be discontinued. If there is an absolute decrease in the shortening fraction of $>10\%$ or the shortening fraction is below 29%, then doxorubicin will be discontinued. Doxorubicin should also be discontinued if the patient develops Grade 3 or 4 left ventricular systolic dysfunction (symptomatic CHF). If doxorubicin is discontinued for the above changes in LVEF, olaratumab should also be discontinued.

The diagnostic method used at baseline for cardiovascular assessments (for example, ECHO or MUGA scans) should be the same method used throughout the study, unless there is clinical or instrumental evidence that further investigations are needed.

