## 5.2. General Considerations

Statistical analysis of this study will be the responsibility of Eli Lilly and Company (Lilly). The analyses for this study will be descriptive, except for possible exploratory analysis as deemed appropriate. Data analyses will be provided by dose groups and for all study patients combined wherever appropriate. For continuous variables, summary statistics will include number of patients, mean, median, standard deviation, minimum, and maximum. Categorical endpoints will be summarized using number of patients, frequency, and percentages. Unless otherwise specified, missing data will not be imputed.

The interpretation of the study results will be the responsibility of the investigator with the Lilly Clinical Research Physician (CRP)/Clinical Research Scientist (CRS), pharmacokineticist, and statistician. The CRP or CRS and statistician will also be responsible for the appropriate conduct of an internal review for both the final study report and any study-related material to be authorized by Lilly for publication.

Exploratory analyses of the data not described below will be conducted as deemed appropriate.

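### SAP 5.9.4 tabulates ECHO/MUGA only by time point, although children who meet a cardiac limit leave the trial: later summaries understate the decline and no table gives the proportion who ever met a limit

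*SAP*

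**What the plan says.** SAP 5.9.4 states: "Electrocardiogram, Echocardiogram(ECHO)/MUGA measurements will also be summarized at each assessment time point using summary statistics". The next sentence adds: "Listings of vital signs, ECG, ECHO/MUGA and data will be provided". SAP 5.2 defines the content of such a summary: "summary statistics will include number of patients, mean, median, standard deviation, minimum, and maximum". Section 5.9.4 names change from baseline for vital signs; whether it extends to ECHO/MUGA is left unclear. Laboratory data, one section earlier, get a patient-level worst-value summary: "The shifts in CTCAE toxicity grading from baseline to worst postbaseline". ECHO/MUGA has no counterpart.

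Protocol 7.2.4.2.2 sets individual limits. For LVEF: "If there is a decrease in LVEF to or below 40% or an absolute decrease of 20%, then doxorubicin will be discontinued". For shortening fraction, doxorubicin stops on an absolute fall of more than 10%, or when "the shortening fraction is below 29%, then doxorubicin will be discontinued". Protocol 7.2.2 then says: "If any study drug is discontinued (olaratumab or chemotherapy), the patient will be discontinued from the trial". On the late scan, 7.2.4.2.2 says: "If doxorubicin cardiotoxicity has been observed, an ECHO or MUGA should be performed at the 30-day follow-up visit". Extra scans are allowed when clinically indicated or at the investigator's discretion.

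**The concern.** Whether an LVEF value exists at a time point depends partly on LVEF. A child who meets a limit contributes to the scan that triggered the stop and to no later on-treatment scan. At 30 days the selection runs the other way, because scans are requested for affected children and are otherwise discretionary. A row of visit means read from left to right therefore compares different groups of children.

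The protocol's limits are also individual changes or thresholds, which by-visit statistics do not count across visits. The question a reader will ask is what proportion of children given olaratumab plus doxorubicin had a fall large enough to stop treatment. No planned table answers it. ECHO/MUGA is a named safety analysis in protocol 10.4, and protocol 6.2 says the combination arms are to inform dose choice for later studies.

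**Working it through.** The plan states no cardiac rate, target or precision, so there is no figure to reproduce. The check compares the texts and then illustrates the size.

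**1. Who contributes at each time point**

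| Time point | Children with a value |
|---|---|
| Scan at which a limit is met | Everyone still on study, including the affected child |
| Later on-treatment scans | Those who have not met a limit |
| 30-day scan | Mainly affected children, plus discretionary scans |

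**2. Worked example.** From protocol 6.2: about 20 evaluable patients per arm. Assumed, not in the documents: every child starts at LVEF 62%; 4 fall by 22 points to 40% (2, 1 and 1 at scans 1, 2 and 3); the rest are stable; no other dropout; a fall would persist.

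Mean = (62 × unaffected + 40 × affected) / n.

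With removal:
- Scan 1: (62×18 + 40×2)/20 = 59.8
- Scan 2: (62×17 + 40×1)/18 = 60.8
- Scan 3: (62×16 + 40×1)/17 = 60.7

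If affected children stayed in:
- Scan 1: 59.8
- Scan 2: (62×17 + 40×3)/20 = 58.7
- Scan 3: (62×16 + 40×4)/20 = 57.6

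The observed mean rises after scan 1 although more children are affected. A 30-day mean from affected children alone would be 40. The by-visit minimum is 40 at all three scans.

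The patient-level figure is 4/20 = 20%. Its Clopper-Pearson 90% limits are the 5% point of Beta(4, 17) and the 95% point of Beta(5, 16), which are 7.1% and 40.1%.

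**3. Simulation with spread and other dropout** (4,000 runs per row). Assumed: baseline mean 62, SD 5, kept above 50; measurement SD 3; affected children fall 22 points at one of three scans; 25% other dropout per interval. Removal follows the protocol's LVEF limits.

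| True share affected | Mean at scan 3, with removal | Mean at scan 3, no removal | True fall from baseline | Hidden | Ever met a limit on study | Met a limit at scan 3, of those scanned |
|---|---|---|---|---|---|---|
| 10% | 61.07 | 59.86 | 2.19 | 1.21 | 6.9% | 3.5% |
| 20% | 59.98 | 57.60 | 4.40 | 2.38 | 13.8% | 7.5% |
| 30% | 58.85 | 55.38 | 6.63 | 3.47 | 21.1% | 11.9% |

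Hidden is the difference between the two means. It is 55%, 54% and 52% of the true fall. With 10% or 40% other dropout the means barely change. The lowest by-visit minimum averages about 40, 36 and 34, against about 50 with nobody affected.

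**4. Two points that affect any patient-level table**

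- *Shortening fraction.* Exclusion 15 in protocol 6.1.2 rules out values below 27%, while 7.2.4.2.2 stops doxorubicin below 29%. A child entering at 27% to below 29% meets the stopping limit with no fall.
- *Scan timing.* Section 7.2.4.2.2 places scans at the end of Cycles 2, 4 and 6. The Part C schedule in Attachment 1 places them before Cycles 1, 3 and 5. Doxorubicin is 2 × 37.5 = 75 mg/m² per cycle and starts in Cycle 2 in Parts A and B but in Cycle 1 in Part C. The first on-treatment scan thus follows 75 mg/m² in Parts A and B (end of Cycle 2) and 150 mg/m² in Part C (before Cycle 3).

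**The case against.** A reader might infer that the planned output cannot show cardiotoxicity at all. The documents do not support that. The triggering scan counts at its own visit; n and the minimum are reported; and each child's values are listed, which is readable at about 20 children per arm. The simulation shows attenuation, not blindness.

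Other tables also help. Reasons for discontinuation are tabulated (SAP 5.4.2). Adverse events are tabulated by term and worst grade, and those leading to discontinuation are listed (SAP 5.9.2). Protocol 8.1.2 requires clinically significant findings to be reported as adverse events, and a fall that ends participation is likely to qualify. This stands as to individual cases. It does not supply the missing rate: a discontinuation reason need not identify a cardiac limit, an adverse-event count depends on reporting and coding rather than on the protocol's limits, and a listing leaves the count to the reader.

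Three further inferences go too far:
- *ECG.* The same selection does not apply. The removal limits are LVEF and shortening fraction, and the 30-day ECG is scheduled for all patients.
- *Unscheduled scans.* SAP 5.9.4 does not exclude them. It simply does not say where they are placed.
- *Dose decisions.* These rest on dose-limiting toxicities, exposure matching and ongoing safety review (protocol 6.2.1, 7.2.3 and 10.8), not on end-of-study visit means.

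**Conclusion.** The point holds as a gap in the summary tables. Later by-visit ECHO/MUGA summaries understate the decline among treated children, the 30-day summary describes a selected group, and no table gives the cumulative proportion who met a protocol limit.

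Under the simulation's assumptions a little over half of the true mean fall at the third scan is hidden, and the share meeting a limit at that scan is a little over half of the share who ever met one on study. These sizes rest on invented LVEF values and on falls that persist. They illustrate direction and mechanism and do not predict this trial. The selection itself follows from the protocol's rules and needs no assumed LVEF values. This is an inexpensive improvement to a descriptive Phase 1 plan, not a defect that undermines its primary objective.

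**What to change.** In SAP 5.9.4, for doxorubicin-treated patients, by dose cohort and overall:

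- (a) Summarise change from baseline in LVEF and in shortening fraction at each scheduled scan, with the number scanned, separately for ECHO and MUGA. Label the 30-day scan as a selected subset.
- (b) Add a worst-postbaseline table over all scans (scheduled, unscheduled and 30-day). Give the number and percentage of patients, with exact 90% CI, who ever met each limit in protocol 7.2.4.2.2, and the cumulative doxorubicin dose at that scan. Show separately patients already below the shortening-fraction limit at baseline.

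The cumulative dose makes Parts A and B comparable with Part C despite their different scan timing. The sponsor should also reconcile the shortening-fraction values in protocol 6.1.2 and 7.2.4.2.2, and the scan timing in 7.2.4.2.2 and the Part C schedule. This review takes no view on which is right.

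The cost is SAP wording and one or two extra tables from data already collected, with no new scans. The reported cardiac figures may look less favourable.
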